### 7.1.1. Liver chemistry stopping criteria

Discontinuation of study intervention for abnormal liver tests is required by the investigator when a participant meets one of the conditions outlined in the algorithm or in the presence of abnormal liver chemistries not meeting protocol-specified stopping rules if the investigator believes that it is in best interest of the participant.

## Phase 1 Liver Chemistry Stopping Criteria – Liver Stopping Event Algorithm

Abbreviations: ALT = alanine transaminase; INR = international normalized ratio; SAE = serious adverse event; ULN = upper limit of normal.

Refer to Section 10.4 for required Liver Safety Actions and Follow up Assessments.

### 7.1.2. QTc Stopping criteria

- If a clinically significant finding is identified (including, but not limited to changes from baseline in QT interval corrected using Fridericia's formula [QTcF] after enrolment, the investigator or qualified designee will determine if the participant can continue the study intervention and if any change in participant management is needed. This review of the ECG printed at the time of collection must be documented. Any new clinically relevant finding should be reported as an AE.

A participant that meets either bulleted criterion below based on average QTc values of triplicate ECGs over a brief recording period (See Section 8.3.3) will discontinue study intervention and will be withdrawn from study intervention.

- QTcF  $> 500$  msec,
- Change from baseline in healthy participants: QTcF  $> 60$  msec

### 7.1.3. Haematology Stopping Criteria

IP will be discontinued for a participant if the following haematology stopping criteria are met (confirmed on two samples taken within 24 hours of each other) or at the discretion of the investigator in consultation with the medical monitor) and participants should be followed up until values are not clinically significant.

- A reduction in haemoglobin to below 8.0 g/dL

- A reduction in neutrophil count to below 500/mm^3 (0.5 × 10^9/L)

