## CONFIDENTIAL

220104  
Protocol Amendment 1 Final

Procedure	Screening	Treatment Period 1			Treatment Period 2		Treatment Period 3			Early Withdrawal	Unscheduled	Notes
	D -14 to -1	D 1	D 2	D 3	D 4	D 5-14	D 15	D 16-17	D 18			
Serial PK sampling: GSK3036656•							X	X				PK samples collected predose (GSK3036656) and after dosing at 0.5, 1, 1.5, 2, 3, 4, 6, 8, 12, 24 hours relative to Day 15 dosing in Treatment Period 3. The Day 15 24 h sample must be taken prior to GSK3036656 dosing on Day 16.  The predose sample to be taken within 30 minutes prior to dose administration.  Blood is drawn for PK analysis at 0.5-4 hours ±5 minutes after dosing.  Blood is drawn for PK analysis at 6-12 hours ±20 minutes after dosing.  Blood is drawn for PK analysis at 24 hours ±1 hours after dosing.
AE review•		←-----→										AEs collected from the start of study intervention until day 18 of Treatment Period 3.
SAE review•		←-----→										SAEs collected from the signing of the ICF until Day 18 of Treatment Period 3.
Concomitant medication review•		←-----→										

AE = adverse event; D = Day; ECG = electrocardiogram; EE = ethinyl estradiol; LNG = levonorgestrel; PK = pharmacokinetic; SAE = serious adverse event.

Assessments performed predose on Day 4 of Treatment Period 2 were considered baseline for GSK3036656 dosing.

- Is used to indicate a study procedure that requires databasing (either in eCRF, laboratory or other third-party vendor).
- Is used to indicate a study procedure that does not require databasing (in source only).
- Participants may be admitted the night before Day 1 and Day 14, but study procedures will commence on the morning of Day 1 and morning of Day 15.

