## 4. STUDY DESIGN

### 4.1. Overall design

This is a Phase 1, open-label, fixed-sequence, 1-way DDI study designed to assess the PK, safety, and tolerability of GSK3036656 and an oral contraceptive containing EE/LNG (Microgynon) when the oral contraceptive is administered alone and in combination with GSK3036656 in healthy female participants of non-childbearing potential.

The study consists of a screening period, check-in to the inpatient facility for a single dose treatment period with Microgynon given alone followed by PK assessments for 72 hours, then discharge. The participant immediately starts a 14-day treatment period with GSK3036656 and is readmitted to the clinic on Day 15 where they receive a single dose of Microgynon in combination with GSK3036656. The participant is discharged from the clinic on Day 18 following completion of the 14-day GSK3036656 treatment period and the 72 hour EE/LNG PK assessments.

Participants will be screened within 14 days before the start of Treatment Period 1. The treatments are as follows:

- Treatment Period 1: Microgynon (0.03 mg EE/0.15 mg LNG) single dose on Day 1 of the treatment period.
- Treatment Period 2: A loading dose of GSK3036656 40 mg on Day 4 then GSK3036656 20 mg od from Day 5 to Day 14
- Treatment Period 3: Microgynon (0.03 mg EE/0.15 mg LNG) single dose coadministered with GSK3036656 20 mg on Day 15 of Treatment Period 3, then GSK3036656 20 mg od alone from Day 16 to Day 17.

Participants will take the single dose of Microgynon in the morning after an overnight fasting (at least 8h) at approximately the same time in Treatment Periods 1 and 3. Participants should remain fasted until at least 4 hours post dose.

Time of dose administration for GSK3036656 should be approximately 24 hours apart.

Blood samples for the analysis of EE, LNG and GSK3036656 will be collected as per SoA.

Safety and tolerability will be assessed by monitoring and recording of AEs, clinical laboratory test results, vital sign measurements, 12-lead ECG results, and physical examination findings.

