### **5.2.2. Laboratory Assessments**

2. Presence of hepatitis B surface antigen at Screening or within 3 months prior to starting study treatment.
3. Positive hepatitis C antibody test result at Screening or within 3 months prior to starting study treatment AND positive on reflex to hepatitis C RNA.
4. Positive HIV-1 and -2 antigen/antibody immunoassay at Screening.
5. Alanine aminotransferase (ALT)  $>1.5 \times \text{ULN}$ . A single repeat of ALT is allowed within a single screening period to determine eligibility.
6. Bilirubin  $>1.5 \times \text{ULN}$  (isolated bilirubin  $>1.5 \times \text{ULN}$  is acceptable if bilirubin was fractionated and direct bilirubin  $<35\%$ ).

7. Any acute laboratory abnormality at Screening which, in the opinion of the investigator, should preclude participation in the study of an investigational compound.
8. Participants with haemoglobin <8.0 g/dL
9. Any Grade 2 to 4 laboratory abnormality at Screening, with the exception of creatine phosphokinase and lipid abnormalities (e.g., total cholesterol, triglycerides, etc), and ALT (described above), excludes a participant from the study unless the investigator provided a compelling explanation for the laboratory result(s) and has the assent of the sponsor. A single repeat of any laboratory abnormality is allowed within a single screening period to determine eligibility.
10. A positive test result for drugs of abuse (including marijuana), alcohol, or cotinine (indicating active current smoking) at Screening or before the first dose of study treatment.

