#### 4.1.2. Baseline Definition

For all endpoints the baseline value (derived for each period) will be the latest pre-dose assessment of respective period with a non-missing value, including those from unscheduled visits. If time is not collected, Day 1, Day 4 and Day 15 assessments are assumed to be taken prior to first dose of the respective period and will be used as baseline.

Unless otherwise stated, if baseline data is missing no derivation will be performed and baseline will be set to missing.

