## 6.2. Appendix 2 Data Derivations Rule

### 6.2.1. Change from Baseline

The change from baseline will be calculated by subtracting the period baseline values from the subsequent post-baseline values. If either the baseline or post-baseline value is missing, the change from baseline is set to missing as well.

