### 6.2.3.1. Laboratory Values

Haematology				
Laboratory Parameter	Units	Category	Clinical Concern Range	
			Low Flag (< x)	High Flag (>x)
Hematocrit	Ratio of 1	Male		0.54
		Female		0.54
		Change from Baseline	Decrease of 0.075	
Haemoglobin	g/L	Male	75	180
		Female	75	180
		Change from Baseline	Decrease of 25	
Lymphocytes	x10  / L		0.8	
Neutrophil Count	x10  / L		1.5	
Platelet Count	x10  / L		100	550
Red blood cell (RBC) count	million/mcL		4.2	6.1
Mean corpuscular volume (MCV)	fl.		80	100
Mean corpuscular hemoglobin (MCH)	picograms (pg)		27.5	33.2
%Reticulocytes	%		0.5	2
Monocytes	%		2	8
Eosinophils	%		1	4
Basophils	%		0.5	1
Clinical Chemistry				
Laboratory Parameter	Units	Category	Clinical Concern Range	
			Low Flag (< x)	High Flag (>x)
Calcium	mmol/L		2	2.75
Creatinine	%	Change from Baseline		Increase of 30%
Glucose	mmol/L		3	11
Potassium	mmol/L		3	5.5
Sodium	mmol/L		130	150
Direct bilirubin	mg/dl		<0.3	<0.3
Total protein	g/dl		6	8.3
Blood urea nitrogen (BUN)/Urea	mg/dl		5	20

Haematology				
Laboratory Parameter	Units	Category	Clinical Concern Range	
			Low Flag (< x)	High Flag (>x)
Creatine phosphokinase (CPK)	mcg/l		10	120
Homocysteine	µmol/L		4	14
Antiphospholipid antibodies	MPL		0	39.9
Sex hormone binding globulin (SHBG)	nmol/L		18	144

Liver Function				
Test Analyte	Units	Category	Clinical Concern Range	
ALT	IU/L	High	$\geq 3x$ ULN	
AST	IU/L	High	$\geq 3x$ ULN	
T Bilirubin	µmol/L	High	$\geq 1.5x$ ULN	

ULN = Upper Limit of Normal; ALT=Alanine Aminotransferase; AST=Aspartate Aminotransferase;

T. Bilirubin=Total Bilirubin

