#### 6.2.3.2. ECG Values

ECG Parameter	Units	Clinical Concern Range	
		Lower	Upper
Absolute			
Absolute QTcF Interval	msec		>450
Absolute PR Interval	msec	< 110	>220
Absolute QRS Interval	msec	< 75	>110
Change from Baseline			
Increase from Baseline QTcF	msec		>60

QTcF=QT Interval corrected for heart rate (Fridericia); PR=Electrocardiographic PR Interval

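### The SAP flags haemoglobin as potentially clinically important only below 75 g/L, 5 g/L lower than the protocol's stopping limit of 80 g/L

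*Protocol*

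**What the plan says.** Protocol Section 7.1.3 discontinues the investigational product on "A reduction in haemoglobin to below 8.0 g/dL". The value must be confirmed on a second sample within 24 hours, or the investigator may stop at discretion in consultation with the medical monitor.

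SAP Section 6.2.3.1 sets the haemoglobin PCI limits in g/L: below 75 or above 180 (the same for both sexes), plus a change category, "Decrease of 25". For that category, SAP Section 4.1.2 says "the baseline value (derived for each period) will be the latest pre-dose assessment of respective period", and SAP Section 6.2.1 says "The change from baseline will be calculated by subtracting the period baseline values from the subsequent post-baseline values". SAP Section 6.2.4 ends Treatment Period 2 at the Day 15 predose point and starts Treatment Period 3 with the Day 15 dose. Treatment on GSK3036656 is therefore split across two baselines, Day 4 and Day 15. The footnote to the protocol's Schedule of Activities (Section 1.3) names one baseline for the drug: "Assessments performed predose on Day 4 of Treatment Period 2 were considered baseline for GSK3036656 dosing".

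The incidence of haematology PCI values in each treatment period is a secondary safety endpoint (Protocol Section 3, Table 3). SAP Section 4.3.2.2.3 tabulates it test by test.

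**The concern.** A value low enough to stop dosing should not fall outside the definition of potential clinical importance for the same test. For haemoglobin it can, because the PCI limit lies below the stopping limit.

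Reduction in red cells is the first risk listed for GSK3036656 in Protocol Table 2, with animal findings and a possible downward haemoglobin trend in the first-in-human study. The haemoglobin PCI row is the most direct tabulated read-out of that risk. Protocol Table 2 already uses PCI in this way: it reports that no first-in-human value met PCI when describing the declines as not clinically relevant. If a reader of this study's report draws the same reassurance from an empty haemoglobin row, that row should at least include every value below the protocol's own limit.

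**Working it through.** **Inputs.** Stopping limit 8.0 g/dL (Protocol 7.1.3). PCI low flag 75 g/L and PCI decrease 25 g/L (SAP 6.2.3.1). Scheduled haematology at Screening, Day 1, Day 4, Day 15 and Day 18, with the Day 1, 4 and 15 samples taken predose (Protocol 1.3). First GSK3036656 dose on Day 4; the protocol ends dosing with "then GSK3036656 20 mg od alone from Day 16 to Day 17".

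**Gap between the limits.** 8.0 g/dL × 10 = 80 g/L, and 80 − 75 = 5 g/L. Values from 75.0 to 79.9 g/L are below the stopping limit but not below the PCI low flag.

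**What the change category recovers.** Reading it as a fall of 25 g/L or more, a value is missed if period baseline < value + 25:

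- value 75.0: missed if baseline < 100.0 g/L
- value 77.5: missed if baseline < 102.5 g/L
- value 79.9: missed if baseline < 104.9 g/L

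Reading it as a fall of more than 25 only adds the boundary values themselves.

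**Day 15 predose.** This is the only scheduled haematology sample between the first and last GSK3036656 doses. Its period baseline is Day 4, so a miss needs a Day 4 value below 104.9 g/L, before any GSK3036656. Exclusion 8 removes only "Participants with haemoglobin <8.0 g/dL", so it admits 80 g/L and above. Exclusion 9 (Grade 2 to 4 abnormalities) may set a higher floor, but it can be set aside with an explanation and sponsor assent, and the documents give no haemoglobin grade cut-points.

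**Day 18.** The baseline is now Day 15. A value of 79.9 is missed if Day 15 < 104.9. Day 15 in turn goes unflagged if Day 4 < Day 15 + 25, so the Day 4 value can be anything below 104.9 + 25 = 129.9 g/L. Example: Day 4 = 122, Day 15 = 98, Day 18 = 79 g/L.

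- Period 2 fall: 122 − 98 = 24, below 25
- Period 3 fall: 98 − 79 = 19, below 25
- Absolute flag: 79 is not below 75
- Total fall: 122 − 79 = 43 g/L, ending below the stopping limit, with no haemoglobin flag

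**Comparison with the other stopping limits (absolute values).**

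- Neutrophils: PCI below 1.5, stop below 0.5 × 10⁹/L. PCI is reached first.
- ALT: 3×ULN for both (Protocol 10.4, SAP 6.2.3.1).
- QTcF: PCI above 450, stop above 500 msec. PCI is reached first.
- Haemoglobin: PCI below 75, stop below 80 g/L. The stopping limit is reached first.

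The contrast does not extend to change in QTcF. The SAP row "Increase from Baseline QTcF" uses the same period baseline, so 375 (Day 4), 410 (Day 15) and 440 msec (Day 18) gives +35 and +30, neither above 60, with 440 not above 450. Yet the rise from Day 4 is +65 msec.

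**Other haematology rows.** Haemoglobin (g/L) = red-cell count (10¹²/L) × MCH (pg). The SAP low flags are 4.2 and 27.5, and 4.2 × 27.5 = 115.5 g/L. Any haemoglobin below 115.5 g/L therefore puts the red-cell count below 4.2 or MCH below 27.5 in the same sample, and one of those rows flags. They would flag equally at 115 and at 79 g/L.

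**The case against.** The strongest reply is that PCI flags and stopping rules serve different purposes, that neither document requires one to be at least as strict as the other, and that almost nothing is lost. Several parts of this stand:

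- The overall haematology PCI endpoint does not miss the participant, because the red-cell count or MCH row flags. What remains is the haemoglobin row alone.
- The stopping criterion needs a confirming sample unless the investigator acts at discretion. A single value of 75.0 to 79.9 g/L is below the limit but need not by itself trigger a stop.
- If doses remain, a confirmed stop is recorded with haematology stopping criteria as the sub-reason (Protocol 7.1), and discontinuation reasons are summarised (SAP 6.1.1). This does not help for Day 18, since the last dose is on Day 17. Such a value is uncounted in the row, but no stop has been missed.
- The participant would probably appear in the grade-increase tables (SAP 4.4.1.1), and as an adverse event if the change is judged clinically significant (Protocol 8.3.4).
- Participants must be healthy or compensated on laboratory evaluation. The first-in-human repeat-dose mean change was −4.9 g/L (−1.5 on placebo), no value met PCI, and Study 201214 showed no significant haemoglobin trend.
- Moving the flag does not cure the baseline reset. A course of 125, 101, 80 g/L (falls of 24 and 21, total 45) is unflagged before and after the change.

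These points limit the size of the problem. They do not explain why haemoglobin, alone among the absolute stopping limits, has a PCI limit that a participant can pass below the stopping limit without reaching.

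**Conclusion.** The concern holds and is minor. The two limits differ by 5 g/L in the wrong direction. A value of 75.0 to 79.9 g/L goes uncounted in the haemoglobin PCI row when the period baseline is below 100.0 to 104.9 g/L. The resulting Day 4 ceiling is 104.9 g/L for a miss at Day 15 and 129.9 g/L for a miss at Day 18. Few or no cases are expected among about 20 participants. Site stopping decisions, the overall haematology PCI incidence and the primary pharmacokinetic analysis are unaffected.

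This rests on the SAP limits being applied as tabulated and on period baselines being used for the change category, as SAP Sections 4.1.2 and 6.2.1 state. How far exclusion 9 narrows the Day 15 case cannot be settled from the documents.

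**What to change.** In SAP Section 6.2.3.1, change the haemoglobin low flag from <75 to <80 g/L. Every value below the Protocol 7.1.3 limit is then counted in the haemoglobin row whatever the period baseline; in the 122, 98, 79 example the Day 18 value is flagged. The cost is one limit in one SAP table, with no new data, and the haemoglobin PCI count would rise by few or none.

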#### **7.1.4. Study Intervention Restart or Rechallenge After Liver Stopping Criteria Are Met**

Study intervention restart or rechallenge after liver chemistry stopping criteria are met by any participant in this study are not allowed.

### **7.2. Participant discontinuation/withdrawal from the study**

A participant may withdraw from the study at any time at the participant's own request for any reason (or without providing any reason).

A participant may be withdrawn at any time at the discretion of the investigator for safety, behavioral, compliance or administrative reasons.

Investigators will attempt to contact participants who do not return for scheduled visits or follow-up.

At the time of discontinuing from the study, if possible, an ED visit should be conducted, as shown in the SoA. See SoA for data to be collected at the time of study discontinuation and follow-up and for any further evaluations that need to be completed.

The participant will be permanently discontinued from the study intervention and the study at that time.

All data and samples collected up to and including the date of withdrawal of/last contact with the participant will be included in the study analyses. If the participant withdraws consent for disclosure of future information, the sponsor may retain and continue to use any data collected before such a withdrawal of consent.

If a participant withdraws from the study, the participant may request destruction of any samples taken and not tested, and the investigator must document this in the site study records.

The primary reason for participant discontinuation/ withdrawal from the study will be documented in the eCRF based on the list below:

Reasons	Additional items/Sub-reasons
AE	
Lost to follow-up	Subject Relocated Subject was Incarcerated Other, specify Unknown
Participant Reached Protocol-Defined Stopping Criteria	Liver chemistry stopping criteria QTc Stopping criteria Haemotology stopping criteria
Physician Decision	Specify
Pregnancy	
Protocol Deviation	Specify
Site Terminated by Sponsor	
Study Terminated by Sponsor	
Withdrawal by Participant	Burden of Procedure Participant Relocated Other
Other	Specify
Death	

Participants who are withdrawn from the study because of AEs/SAEs must be clearly distinguished from participants who are withdrawn for other reasons. Investigator will follow participants who are withdrawn from the study due to an AE/SAE until the event is resolved (see Section [10.3.4.5](#)).

### 7.3. Lost to follow-up

A participant will be considered lost to follow-up if the participant repeatedly fails to return for scheduled visits and is unable to be contacted by the study site.

The following actions must be taken if a participant fails to return to the clinic for a required study visit:

- The site must attempt to contact the participant and reschedule the missed visit as soon as possible, counsel the participant on the importance of maintaining the assigned visit schedule and ascertain whether the participant wishes to and/or should continue in the study.
- Before a participant is deemed lost to follow-up, the investigator or designee must make every effort to regain contact with the participant (where possible, [3] telephone

calls, and if necessary, a certified letter to the participant's last known mailing address or local equivalent methods). These contact attempts should be documented in the participant's medical record.

- Should the participant continue to be unreachable, the participant will be considered to have withdrawn from the study.

## 8. STUDY ASSESSMENTS AND PROCEDURES

- Study procedures and their timing are summarized in the Schedule of activities (SoA) [Table 1](#). Protocol waivers or exemptions are not allowed.
- Adherence to the study design requirements, including those specified in the SoA, is essential and required for study conduct.
- All screening evaluations must be completed and reviewed to confirm that potential participants meet all eligibility criteria. Subjects who have signed informed consent but are not eligible to proceed should be recorded in the eCRF with a status of 'screen failure'.
- Procedures conducted as part of the participant's routine clinical management [(e.g., blood count)] and obtained before signing of the ICF may be utilized for screening or baseline purposes provided the procedures met the protocol-specified criteria and were performed within the timeframe defined in the SoA

The maximum amount of blood collected from each participant over the duration of the study, including any extra assessments that may be required, will not exceed 160 mL.

Repeat or unscheduled samples may be taken for safety reasons or for technical issues with the samples.

### 8.1. Administrative and baseline procedures

#### 8.1.1. Collection of demographic data

Record demographic data such as date of birth, sex, race, and ethnicity in the participant's eCRF.

Collection of sex, race and ethnicity data is necessary to assess and monitor the diversity of the trial participants, and to determine if the trial participants are truly representative of the impacted population.

#### 8.1.2. Medical history

Obtain the participant's medical history by interviewing the participant and/or review of the participant's medical records. Record any pre-existing conditions, signs and/or symptoms present prior to the first dose of study interventionin the eCRF.

## 8.2. Efficacy assessments

Efficacy assessments are not evaluated in this study.

## 8.3. Safety assessments

Planned timepoints for all safety assessments are provided in the SoA.

### 8.3.1. Physical examination/history directed physical examination

- A complete physical examination will include, at a minimum, assessments of the skin, CV, respiratory, gastrointestinal, and neurological systems. Height (at Screening) and weight (at all scheduled timepoints) will also be measured and recorded.
- A brief physical examination will include, at a minimum, assessments of the skin, lungs, CV system, and abdomen [liver and spleen].
- Investigators should pay special attention to clinical signs related to previous serious illnesses.

